#### 6. RESEARCH QUESTION AND OBJECTIVES

This study is intended to assess the following items, etc. for the safety and effectiveness of Vfend 200 mg for Intravenous Use, Vfend Tablets 50 mg, Vfend Tablets 200 mg, and Vfend Dry Syrup 2800 mg (hereinafter referred to as product) in daily clinical practice for prophylactic administration of this product for invasive fungal infections in children and adults and review the necessity for further special investigation and post-marketing clinical study.

- Unknown adverse reactions including those associated with long-term use
- Occurrence of adverse reactions under actual clinical settings including long-time use
- Factors considered to affect the safety and effectiveness of this product

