2.1. Study Design

This study is a prospective multicenter cohort study conducted in patients receiving this product. Pediatric and adult patients who were treated with this product for the purpose of prophylactic administration of this product for invasive fungal infections (IFI) at the commencement of treatment with this product will be included in the study. The observation period shall start on the day of initiation of Vfend treatment and end on the day of completion of treatment; provided that the patients will be followed until the last day of the study period as long as possible if the treatment prolongs. The target sample size is set to be 200 patients in total, 100 patients each for children and adults. The rationale for target sample size is shown below. With hepatic toxicity and visual events considered as major investigation items, tally the occurrence status for patients who developed events related to major investigation items and evaluate the differences in patient background, dose, etc. between patients who can continuously receive treatment with this product and patients who must discontinue treatment with this product.

Rationale for sample size

The sample size is 100 patients each for children and adults, 200 patients in total.

Safety perspectives:

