8.1.4. Analysis of Period Data (Time to Event Onset)

The median, first quartile, and third quartile by Kaplan-Meier method will be calculated. In addition, Kaplan-Meier plots will be prepared.

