- Change in treatment with Vfend: If multiple types of change in treatment with Vfend are reported, one of discontinuation, temporarily discontinued, dose reduction, dose increase or no change, in descending order of precedence, will be adopted.
- Outcome: The outcome of the last occurring event will be used.
- Safety specifications

The number and proportion of patients with events will be tabulated. In addition, the number and proportion of patients with safety specifications by change in treatment with Vfend and outcome will be tabulated by SOC and PT.

• Major investigation items

The number and proportion of patients with major investigation items will be tabulated by SOC and PT. In addition, the number and proportion of patients with major investigation items will be tabulated by SOC and PT for each of the following items.

- Change in treatment with Vfend [discontinuation, temporarily discontinued, dose reduction, dose increase, no change]
- Outcome [not recovered, recovered with sequela, recovering, resolved/recovered, unknown]
- Age (1) [<15 years, ≥ 15 years]

Furthermore, in order to examine the difference between patients who discontinued treatment and those who did not by major investigation item, patients with major investigation items will be tabulated by patient background factor, status of discontinuation/completion, concomitant medication, and status of administration.

• Timing of onset of adverse drug reactions

The number of patients with adverse drug reactions will be tabulated by SOC and PT by timing of initial onset of adverse drug reactions. Categories of timing of onset will be every 30 days. However, if there are many adverse drug reactions that occur at an early stage, the analysis will be performed by subdividing the category of the first 30 days as necessary. Major investigation items will be analyzed in the same manner.

For major investigation items, time to event onset will be summarized for each patient in accordance with Section 8.1.4 with the initial onset of the major investigation item considered as an event. Patients without adverse drug reactions will be right-censored after the observation period + follow-up period (28 days) of this study.

• Relationship between concomitant medications and development of adverse drug reactions

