8.2.3.5. Exploratory Analysis

The following exploratory analysis will be performed for factors affecting safety.

- In patients treated for ≥180 days in the safety analysis set, the number and proportion of patients with adverse drug reactions by timing of onset of initial event (<180 days, ≥180 days) will be calculated by SOC and PT.
- The number and proportion of patients with adverse drug reactions will be tabulated by SOC and PT by factor with a risk ratio of ≥ 2 or ≤ 0.5 .
- In patients determined to have leukemia as an indication for transplantation, the number and proportion of patients with adverse drug reactions will be calculated by SOC and PT for each of acute lymphocytic leukemia, acute myeloid leukemia, and others (including chronic leukemia).

An additional analysis may be performed as necessary. The exploratory analysis will be reported only when results giving important interpretation are obtained.

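### The 30-day onset table for adverse drug reactions gives counts with no number under observation, so it cannot show whether risk changes with longer use

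*SAP*

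**What the plan says.** SAP 8.2.3.1, under timing of onset: "The number of patients with adverse drug reactions will be tabulated by SOC and PT by timing of initial onset of adverse drug reactions". On the bands: "Categories of timing of onset will be every 30 days", with an option to subdivide the first 30 days. For hepatic toxicity and visual events: "Major investigation items will be analyzed in the same manner". Most neighbouring safety tables in 8.2.3.1 and 8.2.3.2 specify both number and proportion; this one specifies the number only.

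Follow-up differs between patients. SAP 2.1: "The observation period shall start on the day of initiation of Vfend treatment and end on the day of completion of treatment". SAP 8.2.3 adds 28 days for the safety tabulations and cuts them at 31 October 2018.

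A censoring-aware analysis exists for two event groups: "For major investigation items, time to event onset will be summarized for each patient in accordance with Section 8.1.4". SAP 8.1.4 sets its output: "The median, first quartile, and third quartile by Kaplan-Meier method will be calculated", plus plots. Numbers at risk are not mentioned.

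The objective concerned is in Protocol section 6: "Unknown adverse reactions including those associated with long-term use".

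**The concern.** A patient whose treatment ended more than 28 days ago cannot add a reaction to a later band. The count in a band is therefore the product of the risk and the number still observed, and the table shows only the product. If the risk is constant, the row still declines. A reader looking for reactions tied to long-term use could take that decline as evidence that risk fades.

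The gap matters for reactions other than hepatic toxicity and visual events. The other safety specifications in SAP 6.1, such as phototoxicity, peripheral neuropathy and renal failure, have no Kaplan-Meier analysis. Their onset timing in 30-day steps comes from this table alone.

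**Working it through.** **Inputs from the documents.** Target 200 patients, 30-day bands, 28-day safety window. The 20% is the presumed incidence of hepatic toxicity in the sample-size rationale. That rationale reproduces: with 200 patients at 20%, the exact binomial probability of at least 31 events is 0.957 (at least 32: 0.937), which agrees with the stated 31 at about 95%.

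**Assumptions, not in the documents.**
- A pooled reaction outcome with constant first-onset rate h, reaching 20% by day 180: h = −ln(0.8)/180 = 0.00124 per day, or 3.72 per 100 person-months of 30 days. The 20% is borrowed, because hepatic toxicity itself already has Kaplan-Meier.
- Exponential stopping of treatment, k = ln 2/median, with median 60, 90 or 120 days, independent of the reaction. The documents give no distribution of treatment duration.
- The same rate h in the 28 days after treatment. The calendar cut is not modelled.

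**Formulas.** Number under observation at day t: 200 up to day 28, then 200·exp(−k(t−28)).

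Expected first onsets in a band starting at day a ≥ 30:
200·[h/(h+k)]·exp(28k)·[exp(−(h+k)a) − exp(−(h+k)(a+30))].

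First band: 200·[1−exp(−28h)] + 200·[h/(h+k)]·exp(28k)·[exp(−28(h+k)) − exp(−30(h+k))].

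**Example, median 90 days.** k = 0.00770, h+k = 0.00894, h/(h+k) = 0.1387, exp(28k) = 1.241.
- Days 150–179: 200 × 0.1387 × 1.241 × (0.2615 − 0.2000) = 2.12.
- Days 0–29: 6.82 + 0.47 = 7.30 (before rounding of the parts).
- Ratio: 2.12/7.30 = 29%.

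| Assumed median (days) | Days 0–29 | Days 150–179 | Ratio | Ratio without the 28-day window |
|---|---|---|---|---|
| 60 | 7.30 | 1.25 | 17% | 15% |
| 90 | 7.30 | 2.12 | 29% | 26% |
| 120 | 7.30 | 2.75 | 38% | 35% |

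A different calibration gives much the same answer. With crude incidence over all follow-up fixed at 20%, a 90-day median and the window included, the first and sixth bands are 8.9 and 2.5 (28%).

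**What a denominator does (median 90 days, window included).**

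| Band start (day) | 0 | 30 | 60 | 90 | 120 | 150 |
|---|---|---|---|---|---|---|
| Count | 7.30 | 6.19 | 4.73 | 3.62 | 2.77 | 2.12 |
| Under observation | 200 | 196.9 | 156.3 | 124.1 | 98.5 | 78.2 |
| Count as % of those observed | 3.65 | 3.14 | 3.03 | 2.92 | 2.81 | 2.71 |

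The last band is 29% of the first as a count but 74% as a proportion (2.71/3.65). The remaining drift arises because patients who already had the reaction stay in the denominator and some leave during a band. The person-time rate is 3.72 per 100 person-months in every band.

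**How well other tables substitute.** SAP 8.2.1 and 8.2.2 band completion, discontinuation and treatment period by 30 days up to day 180. Subtraction gives the number on treatment, not the number observed. From day 28 on, the two differ by a factor of 2^(28/median): 1.38, 1.24 and 1.18 for medians of 60, 90 and 120 days. At 90 days that is 63 on treatment against 78 observed at day 150.

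**The case against.** The strongest case on the other side has five parts.

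- **Denominators can be recovered.** The tables in SAP 8.2.1 and 8.2.2 use matching bands, so an alert reader can see that numbers fall. This stands in part: the reconstruction is rough, sits in other tables and omits the 28-day window.
- **The long-term objective does not rest on this table alone.** SAP 8.2.3.1 gives number and proportion by treatment under 180 days against 180 days or longer, and 8.2.3.4 uses treatment-duration groups. This also stands, but those tables classify patients by total duration, not by when the reaction began. The analysis in 8.2.3.5 ("In patients treated for ≥180 days in the safety analysis set") does use onset, but it has a single split at day 180 and is reported only if the result is judged important.
- **Single rows will be sparse.** Under the same model with a 90-day median, a reaction reaching 5% by day 180 has expected counts of 1.7 in the first band and 0.6 in the sixth; at 2% they are 0.7 and 0.2. No trend can be read from such rows with or without a denominator. This stands, and it is why the illustration applies to a pooled outcome and why a separate reaction-free denominator for every SOC and PT is not worth its cost.
- **The study is descriptive.** SAP 4.1 sets no significance level, and no comparison between bands is planned. This stands and limits the severity.
- **Masking of a real rise is not established.** A reader might infer that the table would hide a true late increase. Take a threefold rise from day 150. With the window, the last band against the first is 3.6 against 7.3 at a median of 60 days and 6.1 against 7.3 at 90, but 8.0 against 7.3 at 120 and 10.4 against 7.3 at 180. Even at 90 days it would appear as a jump from 2.8 in the preceding band. The documents give no treatment durations, so the stronger reading is not supported.

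**Conclusion.** The point holds as a minor weakness of presentation. The onset-timing table reports counts without a number under observation while observation ends 28 days after treatment, so counts decline across bands even at constant risk. Outside hepatic toxicity and visual events, the only onset analysis that allows for this is the conditionally reported split at day 180.

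Under the stated assumptions the decline to days 150–179 is to about 17%, 29% or 38% of the first band. The size depends on the assumed treatment durations; the direction does not, as long as patients leave observation over time. The table cannot show whether risk changes with longer use. It does not follow that a late rise would go unseen, nor that the long-term objective has no other support. No sample size or error rate is affected.

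**What to change.** In SAP 8.2.3.1, add to the onset-timing table one row or column with the number of patients still under observation at the start of each band (treatment plus 28 days, cut at 31 October 2018). Give each SOC and PT count as a proportion of that number. Dividing by the whole safety analysis set would not help, because that denominator does not shrink.

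For any adverse drug reaction overall, also give the rate per 100 person-months in each band with an exact 95% CI, or a Kaplan-Meier curve with numbers at risk. This removes the residual drift in the simple proportion.

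The cost is SAP wording and slightly more tabulation. Administration period and onset date are already collected (Protocol 7.3.2 and 7.3.7). The downside is wide intervals in the late bands.

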### 6.1. Safety Specifications

[Important identified risks] Hepatic toxicity, QT prolongation, ventricular tachycardia, ventricular fibrillation, arrhythmia, atrioventricular block complete, visual events, phototoxicity, peripheral neuropathy such as Guillain-Barre syndrome, renal failure, blood disorder, interstitial pneumonia, heart failure, consciousness disturbed

[Important potential risks] None

[Important missing information] Safety of pediatric use

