8.1.2. Analysis of Categorical Data

The frequency (e.g., number of patients) and proportion of each category will be calculated.

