9. LISTINGS

The following listings will be prepared. Listings with [Intext] specified after the table name are in a format which allows attachment to the report.

Listing of patients⁴

⁴: Estimated creatinine clearance and eGFR before administration will be added to the patient listing. Refer to Appendix 10.3 for calculation method.

- Listing of patients with adverse events
- Listing of patients with adverse drug reactions
- Listing of patients with adverse drug reactions among pediatric patients
- Listing of patients with adverse drug reactions among elderly patients
- Listing of patients with adverse drug reactions among patients with hepatic dysfunction
- Listing of patients with adverse drug reactions among patients with renal dysfunction
- Listing of patients with adverse drug reactions among patients excluded from the safety analysis set
- Listing of patients with serious adverse drug reactions [Intext]
- Listing of deaths [Intext]
- List of events corresponding to safety specifications
- List of adverse drug reactions falling under safety specifications [Intext]
- Listing of laboratory values
- Listing of patients evaluated for effectiveness
- Listing of the status of treatment of Vfend and plasma voriconazole concentration
- List of contraindicated patients
- Listing of prior treatment (antifungal agents administered for prophylaxis of invasive fungal infections)
- Listing of other reasons for discontinuation [Intext]
- Listing of concomitant medications by patient [Intext]

Furthermore, tables corresponding to appendix tables for periodic safety report (PSUR) and application for reexamination will be prepared in accordance with the notification.

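### Time to first hepatic or visual reaction is summarised only by Kaplan-Meier quartiles and a plot; a cumulative risk at fixed days with a 95% CI would be more informative at little cost (minor).

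*SAP*

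**What the plan says.** SAP 8.2.3.1, under timing of onset, states for the two major investigation items (hepatic toxicity and visual events) that "time to event onset will be summarized for each patient in accordance with Section 8.1.4 with the initial onset of the major investigation item" as the event. SAP 8.1.4 defines the output: "The median, first quartile, and third quartile by Kaplan-Meier method will be calculated", together with Kaplan-Meier plots. Neither section mentions a confidence interval or an estimate at a set day. The exact-interval rule in SAP 8.1.3 concerns proportions and applies only where an interval is calculated. On censoring, "Patients without adverse drug reactions will be right-censored after the observation period + follow-up period (28 days) of this study".

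Three other outputs bear on timing:

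- **30-day table (SAP 8.2.3.1).** "The number of patients with adverse drug reactions will be tabulated by SOC and PT by timing of initial onset of adverse drug reactions", in 30-day categories, with the major items handled the same way. SAP 8.1.2 may add the percentage: "The frequency (e.g., number of patients) and proportion of each category will be calculated".
- **Day-180 split (SAP 8.2.3.5).** This gives "the number and proportion of patients with adverse drug reactions by timing of onset of initial event", but only in patients treated for at least 180 days, by SOC and PT.
- **Age.** SAP 8.2.3.1 splits the number and proportion with major items at 15 years. It does not apply that split to time to onset.

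**The concern.** A Kaplan-Meier first quartile exists only once the estimated cumulative risk reaches 25%; the median needs 50% and the third quartile 75%. Protocol 7.5.2 presumes 20% for hepatic toxicity and 5% or more for visual events. The chosen statistics are therefore poorly matched to the expected event rates: the table may show quartiles as not reached, or a late day with no indication of how uncertain it is.

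The stake is modest but real. Reactions under long-term use are a stated objective (Protocol 6), and safety in children is listed as missing information (Protocol 6.1). Yet no planned number gives the risk of a first hepatic or visual reaction by a given day, with its uncertainty, for all patients.

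**Working it through.** **Inputs from the documents.** n = 200, with 100 children and 100 adults (Protocol 7.5.1). Hepatic incidence 20%. Visual incidence 5% or higher; earlier studies gave 12.0%, 4.4% and 42.9%, the last in Japanese children (Protocol 7.5.2). Censoring at end of treatment + 28 days.

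**Assumptions (not in the documents).** Exponential treatment length with median 60 or 120 days, so μ = ln 2/60 = 0.01155 or ln 2/120 = 0.00578 per day. Onset is either early (exponential, mean 20 days, in a susceptible fraction s) or at constant hazard λ. Both are tuned to the stated crude incidence.

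**1. The plan's own figure.** P(X ≥ 31 | 200, 0.20) = 0.957, which agrees with the stated probability of about 95%.

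**2. Crude check.** P(X ≥ 50 | 200, 0.20) = 0.049, so crude hepatic incidence reaches 25% in about 1 study in 20. At 5% incidence the probability is about 2 × 10⁻²¹. Kaplan-Meier can exceed crude incidence under censoring, so steps 3 and 4 are needed.

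**3. Early onset.** The Kaplan-Meier curve levels off at s = crude/[1 − e^(−28/20) × μ/(μ + 1/20)].

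- Hepatic: s = 0.20/0.954 = 21.0%, or 0.20/0.974 = 20.5%. Both lie below 25%. In simulation (2,000 runs) the first quartile is reached in 6-9% of runs, and the median and third quartile in none.
- Visual at 5% or 12%: no quartile is reached.
- Visual with 100 children at 42.9%: s in children is about 45% or 44%, so their first quartile is reached in essentially every run. With adults at 5% the overall plateau is about (45 + 5)/2 = 25%; with adults at 12% it is about (45 + 12.6)/2 = 29%. The overall first quartile is then reached in about 43-89% of runs.

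**4. Constant hazard, hepatic.** Solve 1 − e^(−28λ) × μ/(μ + λ) = 0.20. This gives λ = 0.00207 (median 60) or 0.00120 (median 120) per day.

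- First quartile: ln(4/3)/λ ≈ day 139 or 239. In simulation it is reached in over 99% of runs, at about day 138 or 238, with 43-45 at risk and a typical 95% CI of day 94-215 or 161-365. None of that precision would be reported.
- Median: reached in 65% or 76% of runs, at about day 301 or 543.
- Visual first quartile: reached in 23-28% of runs at 5% incidence (4-5 at risk) and 83-88% at 12% (14-16 at risk).

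**5. Do the 30-day counts fill the gap?** Compare the cumulated count over 200 with 1 − e^(−λt). For t > 28, the expected crude proportion is 1 − e^(−28λ) + e^(−28λ) × [λ/(λ + μ)] × [1 − e^(−(λ+μ)(t−28))].

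| Hepatic, constant hazard | Median 60: crude vs KM | Median 120: crude vs KM |
|---|---|---|
| Day 90 | 14% vs 17% | 9% vs 10% |
| Day 180 | 18% vs 31% | 14% vs 19-20% |

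At Day 30 the two agree. Under early onset they stay within about 1 point through Day 180 (20% vs 21%). The Day-180 split of SAP 8.2.3.5 would cover about 200 × 0.5^(180/60) = 25 or 200 × 0.5^(180/120) = 71 patients.

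**6. What the added rows would show (hepatic, constant hazard).**

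| | Median 60: risk (95% CI), at risk | Median 120: risk (95% CI), at risk |
|---|---|---|
| Day 90, n = 200 | 17% (12-24%), 81 | 10% (7-16%), 125 |
| Day 180, n = 200 | 31% (22-43%), 24 | 20% (14-27%), 67 |
| Day 180, n = 100 | 31% (19-48%), 12 | 19% (11-31%), 33 |

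**The case against.** The strongest reply is that nothing here is wrong. SAP 4.1 declares all testing exploratory, SAP 4.2 has no decision rules, and Protocol 7.7 promises no time-to-event analysis for safety, so the Kaplan-Meier summary already goes beyond the protocol. The plot shows the censoring-adjusted risk at every day, and the 30-day counts over a known denominator cover the days of interest. The two weaknesses also do not coincide for hepatic toxicity: with early onset the quartiles fail but the counts suffice, and with constant hazard the first quartile is reached. Early onset is the pattern the SAP prepares for, since it allows the first 30 days to be subdivided.

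Most of this stands, and it limits the point to a minor one. What remains is that neither the plot nor the counts carries a stated interval, and that the counts fall short at later days if onset is spread over time.

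Three stronger readings are tempting, and the documents do not support them:

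- **That the quartiles will never be estimable.** They may be, under constant hazard or with pediatric visual incidence near 42.9%. The 5% figure is a floor.
- **That reactions in children are neglected.** The number and proportion of major items, all reactions and serious reactions are split at 15 years, and SAP 9 adds a pediatric listing. The SAP's change record shows that analyses in children, and subgroup analyses of major items, were reduced on purpose, the latter because of small numbers.
- **That the absence of a separate rule for death before onset undermines the curve.** No death rate is given. Assuming 10-30% mortality by Day 180, the largest shift under constant hazard is from 31% to 26.7%, inside the 22-43% interval. Under early onset it is below 1 point.

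**Conclusion.** The point holds as a minor improvement. For the two major investigation items, the specified quartiles suit the presumed incidences of 20% (hepatic) and 5-12% (visual) poorly. They will usually be unreached under early onset; under constant hazard the hepatic first quartile comes late and without stated precision. The existing counts and plot cover much of the early-onset case. The material gap is the missing interval and, under constant hazard, an understatement of Day-180 hepatic risk by about 13 points (31 − 18) or 5-6 points (19-20 against 14) if the counts are read as cumulative risk.

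These sizes rest on assumed treatment-length and onset distributions and are sensitive to them. With a mean onset of 30 rather than 20 days and treatment medians of 60 or 100 days, the hepatic first quartile is reached in 13-23% of runs instead of 6-9%. The lack of a fixed-day estimate with a CI for all patients does not depend on these assumptions.

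**What to change.** In SAP 8.2.3.1, for hepatic toxicity and for visual events separately, add the Kaplan-Meier cumulative proportion with first onset by Days 30, 60, 90 and 180, with 95% CI and number at risk, in all patients. Describe it as risk while under observation (treatment + 28 days), and note that censoring is tied to the end of treatment. Show the same rows by Age (1) (<15, ≥15 years) descriptively, where the numbers at risk allow. Keep the quartiles, plots and 30-day counts. An analysis with death as a competing event is optional, as a sensitivity analysis only.

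The cost is a few lines of SAP text and a few table rows from data already collected for the planned summary. The drawbacks are wide intervals at late days and within age groups: about 12-33 of 100 still at risk at Day 180 for hepatic toxicity under constant hazard, and about 5 visual events per 100 at 5% incidence. Late-day values also depend on censoring that is linked to treatment.
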